## 46 INTRODUCTION

47 Stiffness after total knee arthroplasty (TKA) occurs when patients have difficulty flexing and  
48 extending their knee for routine activities of daily living. Patients require 67 degrees of knee  
49 flexion during the swing phase of gait, 83 degrees to ascend stairs, 90 degrees to descend stairs  
50 and 93 degrees to rise from a standard chair. When less than 90 degrees of motion is reached  
51 after TKA, the quality of life for patients is substantially decreased since simple activities like  
52 walking can become difficult.

53

54 Despite advancements in surgical technique, implant design and pain management, arthrofibrosis  
55 (i.e., malignant stiffness) remains one of the top five reasons for revision TKA. At the upcoming  
56 2016 American Academy of Orthopaedic Surgeons annual meeting, [name].,  
57 and colleagues will present their data indicating a contemporary arthrofibrosis rate of 5.8 percent  
58 after primary TKA at Mayo Clinic. In addition, 2.8 percent of patients require a manipulation  
59 under anesthesia (MUA). While there are alternatives to MUA, physical therapy shows only  
60 modest gains and surgery is reserved for patients that fail non-operative management. With  
61 MUA, mean flexion improved 35 degrees. However, 5 percent of patients failed to maintain at  
62 least 90 degrees of flexion after the MUA at our institution. More concerning, these results were  
63 similar to the previous decade, where the rate of arthrofibrosis was 5.4 percent, with 2.9 percent  
64 requiring MUA. The only identifiable risk factor for MUA was previous knee operation. Lastly,  
65 a manipulation under anesthesia significantly increased the risk for revision. As one can see, the  
66 incidence of arthrofibrosis following primary TKA has remained unchanged over the past two  
67 decades. With the exponential increase in primary TKAs, arthrofibrosis is a large burden to the  
68 patient, surgeon and entire U.S. health care system (\$8.75 billion annually).

69

70 Preliminary clinical and translational research has indicated that an inflammatory disorder of the  
71 musculoskeletal system may be responsible for post-operative stiffness in some patients.  
72 Although evidence remains limited to animal models, the inflammatory cascade plays a central  
73 role in the formation, and recurrence, of arthrofibrosis, particularly at the time of insult (i.e. time  

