## 79 **PATIENTS AND METHODS**

### 80 ***Study Design***

81 This study is a prospective, multicenter, randomized clinical trial (RCT) designed to evaluate the  
82 use of anti-inflammatory medications for the management of arthrofibrosis following primary  
83 TKA. Patients will be randomly assigned to either the control or experimental group. Both groups  
84 will receive a manipulation under anesthesia (MUA) if flexion is < 90 degrees at 4 –12 weeks  
85 postoperatively. Manipulation under anesthesia is the international standard of care for early  
86 arthrofibrosis. The control group will not receive any IV corticosteroids or PO non-steroidal anti-  
87 inflammatory medications (NSAIDs). The experimental group will receive a single dose of IV  
88 corticosteroids (8 mg IV dexamethasone immediately prior to MUA) and 2 weeks of PO celecoxib  
89 at a dose of 200 mg daily. Many surgeons, including several at the Mayo Clinic, consider the use  
90 of IV corticosteroids and PO celecoxib the standard of care with a MUA.

91

92 ***Patients***

93 Patients will be recruited from sixteen high-volume, academic, tertiary-care referral centers  
94 (Table 1). All enrolling centers have been vetted, as only surgeons that are members of the  
95 prestigious closed Knee Society (representing the top 100 knee surgeons in the world) are  
96 participating. Patients approached for enrollment will have received a primary unilateral TKA  
97 for a diagnosis of osteoarthritis. All primary TKA constructs will have constraint that is less than  
98 that of varus-valgus constraint (VVC). All VVC and hinged TKAs will be excluded. Only  
99 MUAs scheduled between 4 –12weeks postoperatively will be included.

100

101 Institutional Review Board (IRB) approval will be obtained from all respective institutions prior  
102 to initiation of the study. The Mayo Clinic will serve as the coordinating site. Patients will be  
103 excluded from the study if any of the following exist: (1) intolerance to NSAIDs, (2) renal  
104 dysfunction, (3) age < 18 or > 90 years, (4) primary diagnosis of rheumatoid arthritis and (5)  
105 patients with GFR <60 as the cut off for CKD (stage 3 CKD). Use of non-steroidal anti-  
106 inflammatory medications during the first two weeks after manipulation under anesthesia will  
107 exclude patients from participation in this study. However, celecoxib (a non-steroidal anti-  

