108 inflammatory medication) will be provided for those patients randomized to the experimental  
109 group, once daily for fourteen days following the manipulation under anesthesia. Aspirin, used  
110 routinely for DVT prophylaxis post-operatively, did not restrict patients from participation in this  
111 study. Patients who are on NSAIDs prior to MUA, is ok to enroll. Patient demographics were  
112 noted, including age at index arthroplasty, sex, body mass index (BMI), ASA score, and  
113 Charlson Index.

114

115 ***Randomization***

116 Patients will be randomized into one of 2 groups: (1) MUA only (i.e. control group) or (2) MUA  
117 plus 8 mg of IV dexamethasone immediately before MUA, followed by 2 weeks of PO celecoxib  
118 (200 mg daily) (experimental group). Assignment of patients into either group will be made prior  
119 to the initiation of enrollment for the study. Patients will be randomized using a computer  
120 generated (SAS PROC) block randomization schedule to ensure equivalent numbers of patients  
121 in each group over the course of the study in case early stopping is required. The randomization  
122 schedule will be generated by the Mayo Clinic Department of Epidemiology and Biostatistics  
123 with the randomization list provided to the investigators prior to initiation of patient recruitment.  
124 Neither the patient nor the treating physician were blinded the randomization group.

125

126 ***Manipulation Under Anesthesia***

127 Patients will undergo MUA per their institutional protocol. As previously noted, these will be  
128 completed between 4 and 10 weeks postoperatively for flexion < 90 degrees. Patients will  
129 receive sedation per their institutional protocol. Physical therapy (either supervised or  
130 unsupervised) will be prescribed 2 -3 times per week for 4 – 6 weeks thereafter.

131

132 ***Outcome Measures***

133 The primary outcome measure will be knee range of motion, including both passive and active  
134 flexion and extension 6 weeks after the manipulation and 1 year from the date of the TKA.  
135 Secondary outcomes will include comparison of Knee Society Scores (KSS), 12-item Short  
136 Form Survey (SF-12v2), Knee Injury and Osteoarthritis Outcome Score (KOOS), and the  
137 Promise-29 outcome form (Appendices 1-4). Outcomes will be documented pre-MUA, 6 weeks

138 after the MUA, and 1 year after the TKA. A standardize evaluation form will be shared amongst  

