139 all participating sites, and will be used consistently for all patients (Appendix 1-4).

140

141 ***Power Analysis***

142 The mean and standard deviation for sample size calculation were derived from a study by  
143 Yercan et al. In that study, the authors found that the mean ROM following MUA was  $114^\circ \pm$   
144  $16^\circ$ . We hypothesized that a  $10^\circ$  difference in total range of motion would constitute a  
145 clinically significant difference. With a type I error rate of 5%, 108 total patients (54 per arm) are  
146 required to have 90% power to detect this difference. Accounting for a dropout rate of 20%, 65  
147 patients per arm (130 total patients) will be recruited.

148

149 ***Statistical Analysis***

150 All data will be summarized and reported descriptively using appropriate summary statistics,  
151 including mean and standard deviation (SD) for continuous variables, and count and percentage  
152 for categorical variables. The analysis was focused on the two primary study outcomes: range of  
153 motion (total arc of motion as well as angle of terminal knee flexion, measured in degrees), and  
154 subjective outcome (KSS, SF-12v2, KOOS, and PROMIS). Outcomes were compared between  
155 the two study groups using two-sample t-tests if the data are approximately normally distributed;  
156 if the data are not sufficiently normally distributed, non-parametric Wilcoxon rank sum tests was  
157 used. Since the subjects were assigned to the study groups in a randomized manner, no  
158 significant differences between the subjects in the two groups were expected. However,  
159 apparent differences in subject demographics or baseline clinical data were evaluated, and  
160 further analysis was undertaken using multivariable modeling to compare the two groups while

161 adjusting for other important variables. When necessary and appropriate, the analysis was  
162 adjusted for enrolling center. Categorical outcomes were analyzed using chi-square tests and  
163 logistic regression. Separate analyses were performed for the 6-week and 1-year outcomes. All  
164 statistical tests were two-sided and p-values less than 0.05 will be considered significant.

165

166 ***Sources of Funding***

167 This study is partially supported by the Knee Society Branded Multi-Center Randomized Clinical  
168 Trial Grant.

169  
170  
171  
172  
173  
174  
175  
176  
177  
178  
179  
180  
181  
182  
183  
184  
185  
186  

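### Therapy after manipulation can vary from 8 to 18 sessions while the physician knows the arm, leaving the range-of-motion comparison open to co-intervention bias of unknown, possibly small, size

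*Combined protocol and SAP*

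**What the plan says.** The Manipulation Under Anesthesia section has one therapy rule for everyone: therapy, supervised or "unsupervised) will be prescribed 2 -3 times per week for 4 – 6 weeks thereafter". It does not say who chooses within that range, on what basis, or whether the choice is made per site or per patient.

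The Randomization section makes the arm known when that choice is made:

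- The schedule is generated centrally, "with the randomization list provided to the investigators prior to initiation of patient recruitment".
- The trial is open: "Neither the patient nor the treating physician were blinded the randomization group".
- The experimental arm receives manipulation "plus 8 mg of IV dexamethasone immediately before MUA, followed by 2 weeks of PO celecoxib". The arm is therefore evident by the time of the procedure, even to someone without the list.

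Outcome Measures makes range of motion primary at 6 weeks after manipulation and at 1 year after the knee replacement. Statistical Analysis analyses the two times separately. It allows multivariable modelling when demographics or baseline data appear to differ, "adjusting for other important variables. When necessary and appropriate, the analysis was" adjusted for enrolling center. Therapy is not named as a variable there, and it has no row in Table 2 or Table 3. A standardized evaluation form is mentioned, but its appendices are not shown.

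**The concern.** Therapy acts on range of motion, which is the primary outcome, and it fills 4 to 6 of the 6 weeks before the first primary assessment. If knowledge of the arm influences which regimen a patient is prescribed, the difference between arms mixes a drug effect with a therapy effect.

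The direction cannot be predicted. Study Design notes that many surgeons already regard these drugs as standard care with manipulation. A physician of that view might compensate control patients with fuller therapy, or might invest more in experimental patients.

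Variation between sites is a lesser matter. It adds noise, and center adjustment is available. Center adjustment does not correct a choice that follows the arm within a site.

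**Working it through.** **Inputs.** From Manipulation Under Anesthesia: 2 to 3 sessions a week for 4 to 6 weeks. From Power Analysis: difference 10 degrees, SD 16 degrees, 54 per arm, 5% type I error, 90% power. From Statistical Analysis: two-sided tests.

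**The plan's own figure.** n per arm = 2 × [(1.960 + 1.282) × 16 / 10]² = 53.8, rounded up to 54, or 108 in total. This matches the plan. The two-sample t-test with 106 degrees of freedom (noncentral t) has 89.6% power at 54 per arm.

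**Range of therapy.** 2 × 4 = 8 sessions to 3 × 6 = 18 sessions; 18 / 8 = 2.25. This is the spread open to any patient in either arm.

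**Bias.** Suppose fuller therapy is worth *g* degrees more than lighter therapy, equally in both arms, and the share of patients receiving it differs between arms by *q*. The added difference in means is *g* × *q*. The document gives neither quantity, so both are assumed below. The standard error of the difference is 16 × √(2/54) = 3.08 degrees.

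| Assumed *g* (degrees) | Assumed *q* | Bias (degrees) | False-positive rate, no drug effect | Power at a true 10 degrees, bias against the drugs |
|---|---|---|---|---|
| – | – | 0 | 5.0% | 89.6% |
| 2 | 10 points | 0.2 | 5.05% | 88.4% |
| 2 | 20 points | 0.4 | 5.2% | 87.1% |
| 5 | 10 points | 0.5 | 5.3% | 86.4% |
| 5 | 20 points | 1.0 | 6.2% | 82.5% |
| 10 | 10 points | 1.0 | 6.2% | 82.5% |
| 10 | 20 points | 2.0 | 9.9% | 73.1% |

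**Thresholds for a bias from any source.**

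- 2.03 degrees doubles the false-positive rate to 10%. Reaching it needs *q* = 2.03/10 = 20 points at *g* = 10, or 2.03/5 = 41 points at *g* = 5. At *g* = 2 it would need 2.03/2, over 100 points, which is impossible.
- 1.29 degrees against the drugs lowers power to 80%. That needs 1.29/10 = 13 points at *g* = 10, 1.29/5 = 26 points at *g* = 5, or 1.29/2 = 65 points at *g* = 2.

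**Timing.** Therapy ends 6 − 6 = 0 to 6 − 4 = 2 weeks before the 6-week visit. For the 1-year visit the gap depends on when manipulation is done, and the document gives two windows.

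- The Patients section: "MUAs scheduled between 4 –12weeks postoperatively will be included". Therapy ends 8 to 18 weeks after the knee replacement, so 52 − 18 = 34 to 52 − 8 = 44 weeks before 1 year.
- Manipulation Under Anesthesia: "completed between 4 and 10 weeks postoperatively for flexion < 90 degrees". Therapy ends 8 to 16 weeks after, so 36 to 44 weeks before 1 year.

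**The case against.** **The size may be trivial.** Both arms share one permitted range, which limits how far prescriptions can differ while the protocol is followed. In five of the six assumed combinations the false-positive rate is at most 6.2% and power at least 82.5%. The sixth needs the gap between lighter and fuller permitted therapy to be worth 10 degrees, which is the whole difference the trial is sized to detect, together with a 20-point imbalance. The Introduction describes therapy as giving only "modest gains and surgery is reserved for patients that fail non-operative management". This largely stands and is why the point is rated low. The Introduction's remark, however, concerns therapy as an alternative to manipulation, not therapy after it.

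**The estimand.** In an open-label trial of manipulation with and without the drugs, therapy changes that follow from a patient's response can count as part of the strategy's effect. This stands: only a choice driven by knowledge of the arm is bias. The plan defines no estimand that would count such a choice as a drug effect.

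**Recording.** A reader might infer that therapy goes unrecorded. The document does not support that. The form's appendices are not shown, and Statistical Analysis promises descriptive summaries of all data. What can be said is that Tables 2 and 3 have no therapy row. Recording alone would not make the prescription independent of arm.

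**The 1-year result.** A reader might take the 34 to 44 week gap to mean that 1 year is less exposed. That would require therapy gains to fade, which the document does not say. If early motion persists, the bias carries over.

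**Conclusion.** The plan allows therapy to vary 2.25-fold in prescribed sessions, and in mode, while the arm is known, and no rule in the document separates that choice from the arm within a site. The comparison of range of motion at 6 weeks, and possibly at 1 year, is therefore open to co-intervention bias of unknown direction.

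A reader might go further and infer that the arms will receive different therapy, or that 8 against 18 sessions is a difference between arms. The document supports neither. It shows an opportunity for imbalance, not an imbalance, and it gives no effect of therapy after manipulation.

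On the assumed grid the bias is 0.2 to 2.0 degrees, small in five combinations of six. Those figures rest on SD 16, 54 evaluable patients per arm, and a therapy gain equal in both arms; they illustrate and do not estimate. Severity: consider. The case for acting is that the change is cheap, not that harm is shown.

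**What to change.** **Manipulation Under Anesthesia.** Add: *Before its first patient, each site declares one default therapy regimen (mode, sessions per week, number of weeks) within the permitted range and prescribes it to both arms. Deviations for clinical reasons are logged with date and reason.* Sites keep their own practice, and differences between sites remain noise.

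**Evaluation form and Table 3.** Record sessions prescribed and attended to week 6, if the form does not already do so, and report them by arm in Table 3. Keep this descriptive. Deviations and attendance arise after randomization and the drugs may affect them, so they should not be adjustment covariates.

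**Randomization.** Replace giving the list to investigators with: *The list is held centrally by the coordinating site's biostatistics department, and each patient's arm is released only after enrolment.* This mainly protects allocation concealment. It does little for therapy, because the arm is known once dexamethasone is given.

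Requiring an individual therapy order before manipulation is not recommended. It would fix the order before the motion achieved is known, which is a debatable trade-off, and the site default already covers the initial prescription.

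**Cost.** One added sentence, one replaced sentence, a central release step for each of 130 patients, a few form fields if absent, a few table rows, and slightly less freedom to tailor therapy. Later changes by unblinded staff become visible but are not eliminated.

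### Recruiting 65 per arm does not cover 20% dropout: 52 per arm remain, not the 54 the plan requires for 90% power

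*Combined protocol and SAP*

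**What the plan says.** The calculation is in the Power Analysis section of the combined protocol and SAP. It takes a mean range of motion after manipulation of 114 degrees with a standard deviation of 16 from a cited study, and treats 10 degrees of total range of motion as the clinically significant difference. It continues: "With a type I error rate of 5%, 108 total patients (54 per arm) are" "required to have 90% power to detect this difference. Accounting for a dropout rate of 20%, 65" "patients per arm (130 total patients) will be recruited".

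The Statistical Analysis section plans two-sample t-tests, with Wilcoxon rank sum tests if the data are not sufficiently normal. It adds that all "statistical tests were two-sided and p-values less than 0.05 will be considered significant". The 6-week and 1-year outcomes are analysed separately. The plan does not show how it got from 54 to 65, and does not say to which of the two time points the 20% applies.

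**The concern.** A dropout allowance has one purpose: to leave the required number of evaluable patients if the assumed loss occurs. Here one multiplication shows that it does not, because 80% of 130 is 104, below 108. The required number, the dropout rate and the recruitment target therefore cannot all stand.

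At stake is the stated 90% power. If dropout reaches the planned rate, the trial has less power than it claims for the difference it calls clinically significant. Nothing else in the plan makes up the gap: there is no sample-size re-estimation and no replacement of dropouts, and adjustment for baseline variables is planned only if apparent differences emerge.

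**Working it through.** **Inputs.** From Power Analysis: SD 16, difference 10, type I error 5%, power 90%, dropout 20%, recruitment 65 per arm. From Statistical Analysis: two-sided tests, two-sample t-test. From Randomization: equal group sizes.

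**Step 1: reproduce the plan's evaluable number.** By the normal approximation,

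n per arm = 2 × (1.960 + 1.2816)² × 16² / 10² = 53.8, rounded up to 54, or 108 in total.

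This matches the plan exactly. A one-sided test would give 44 per arm, so the plan did use a two-sided test.

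**Step 2: the dropout step.** If a fraction d of recruited patients is lost, recruiting N leaves N × (1 − d), so N must be at least n / (1 − d).

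| Calculation | Per arm | Total |
|---|---|---|
| n / (1 − 0.2) | 54 / 0.8 = 67.5, so 68 | 136 |
| n × (1 + 0.2) | 54 × 1.2 = 64.8, so 65 | 130 |
| Plan | 65 | 130 |

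Only the second line gives the plan's figure. If the total alone is inflated, 108 / 0.8 = 135.

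**Step 3: what 65 per arm leaves.** 65 × 0.8 = 52 per arm, and 130 × 0.8 = 104 in total. The shortfall is 108 − 104 = 4 evaluable patients. The largest loss that still leaves 54 per arm is 1 − 54/65 = 16.9%.

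**Step 4: power** (difference 10, SD 16, two-sided 5%).

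| Evaluable per arm | Normal approximation | t-test (noncentral t) |
|---|---|---|
| 52 | 89.0% | 88.4% |
| 54 | 90.1% | 89.6% |
| 55 | 90.6% | 90.1% |

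Within either column, the drop from 54 to 52 costs about 1.1 points. The rest of the gap between 88.4% and the stated 90% arises because 54 is a normal-approximation answer; for the t-test, 55 is the first number to reach 90%.

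**Step 5: detectable difference.** At 52 per arm, the difference detectable with 90% power by the t-test is 10.27 degrees. By the normal approximation it is 3.2416 × 16 × √(2/52) = 10.17 degrees. Both exceed the 10 degrees the plan set.

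**The case against.** The strongest objection is that this hardly matters. Like for like, the dropout step costs about 1.1 points of power, which is small beside the uncertainty in the SD of 16, taken from a single cited study. At 52 per arm, an SD of about 15.6 instead of 16 would restore 90% for the t-test. That is fair, and it limits how much weight the point carries. It does not make the printed figures agree.

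Three narrower points also have force:

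- **The formula is inferred.** The plan does not say that it multiplied by 1.2. The match (64.8 rounded up to 65) is close, but the shortfall of 104 against 108 does not depend on it. If the authors meant 20% of the evaluable number, the allowance is really for 16.9% of those recruited, and the text still needs correcting.
- **54 is a conventional answer.** Rounding 53.8 up to 54 by the normal approximation is accepted practice. The difference between 54 and 55 is secondary and is not the error described here.
- **The time point is open.** If 20% is the expected loss by 1 year, and the loss at 6 weeks is 16.9% or less, the 6-week comparison keeps its 54 per arm. The shortfall then affects only the 1-year comparison.

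**Conclusion.** The concern holds. The evaluable requirement of 108 is correct by the usual formula; the recruitment target derived from it is not. Under the plan's own 20% dropout, 130 recruited patients leave 104, and power is 88.4% (t-test) or 89.0% (normal approximation) instead of 90%. The correct target is 68 per arm, so recruitment is 3 per arm, or 6 in total, too low.

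This rests on the ordinary reading of dropout as a share of those recruited, on equal loss in the two arms, and on the plan's own SD and difference. It is an error in a stated figure that should be corrected. It does not threaten the validity of the trial.

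**What to change.** Replace the last sentence of the Power Analysis section with one of these:

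1. **Keep 130 and restate the power.** With 65 per arm and 20% dropout, 52 per arm are evaluable, giving 88% power by the two-sample t-test (89% by the normal approximation) to detect 10 degrees with SD 16 at two-sided 5%.
2. **Keep 130 and restate the allowance.** 65 per arm retains 54 per arm if dropout does not exceed about 17%.
3. **Keep 90% power and 20% dropout.** Recruit 68 per arm, 136 in total.

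Whichever is chosen, say which formula was used and to which time point the dropout rate applies. The first two options cost one sentence and a slightly less favourable statement; the third costs 6 more patients.

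If the sponsor chose to prespecify a baseline-adjusted analysis, 90% power could be recovered at 52 per arm. Adjustment reduces the variance by the factor 1 − r², and the factor needed is (10/10.27)² = 0.948, so r must be at least about 0.23. The documents give no baseline–outcome correlation, so this is an assumption to be justified and the correction does not depend on it.

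### Four instruments are secondary in one section and primary in another, and the plan names no deciding test, visit or rule for sharing alpha

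*Combined protocol and SAP*

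**What the plan says.** Under Outcome Measures, ROM is the primary outcome, covering passive and active measurements of "flexion and extension 6 weeks after the manipulation and 1 year from the date of the TKA". Neither visit is ranked above the other. The same section continues "Secondary outcomes will include comparison of Knee Society Scores (KSS), 12-item Short" and goes on to the SF-12v2, KOOS and PROMIS-29, so all four instruments are secondary there.

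Under Statistical Analysis the structure changes: "for categorical variables. The analysis was focused on the two primary study outcomes: range of" "motion (total arc of motion as well as angle of terminal knee flexion, measured in degrees), and" "subjective outcome (KSS, SF-12v2, KOOS, and PROMIS). Outcomes were compared between". Here ROM means total arc and terminal flexion, and the four instruments form a second primary outcome. On visits and thresholds, the section says "logistic regression. Separate analyses were performed for the 6-week and 1-year outcomes. All" "statistical tests were two-sided and p-values less than 0.05 will be considered significant".

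Power Analysis takes 10 degrees in total ROM as the difference of interest, with an SD of 16 degrees: "clinically significant difference. With a type I error rate of 5%, 108 total patients (54 per arm) are" needed for 90% power. It names no visit and no measurement mode.

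The Table 3 shell does not settle the matter. It has a p-value column covering ROM and all four instruments at both visits, and marks none of them as primary.

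**The concern.** The same instruments cannot be both primary and secondary. The ROM endpoint is not fixed either: one section lists flexion and extension in two modes, another lists total arc and terminal flexion, and the sample size uses total ROM alone. A threshold for each test is given. What is missing is any rule for ordering the tests or sharing alpha among them, and any statement of what makes the trial positive.

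Two readings are open, and neither matches the stated design. If one significant primary result is enough, the overall type I error exceeds 5%. If every primary result must be significant, type I error is controlled but power falls below 90%. The ambiguity matters more because, under Randomization, neither patient nor treating physician is blinded. Moving patient-reported scores into the primary set would let success rest on the outcomes most open to expectation effects.

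**Working it through.** **Inputs from the documents.** Difference 10 degrees, SD 16 degrees, two-sided 5%, 90% power, 54 per arm, 65 per arm recruited, 20% dropout (Power Analysis; sidedness from Statistical Analysis). Two ROM variables, four instruments and two visits (Statistical Analysis).

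**Assumptions.** One score per instrument, and one common correlation between tests. The documents give no correlations, so a range is shown. Independence serves only as an upper bound.

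**1. The plan's own figure.** Per arm, n = 2(1.960 + 1.282)² × 16² / 10² = 53.8, so 54. The stated number reproduces, for one test. The two-sample t-test (noncentral t) has power 89.6% with 54 per arm, and 88.4% with the 52 per arm left after 20% dropout from 65 (65 × 0.8 = 52).

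**2. Count of tests.** ROM only: 2 variables × 2 visits = 4. With the instruments: (2 + 4) × 2 = 12. One ROM variable at both visits: 2.

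**3. Chance of at least one false positive if any one result counts.** Under independence this is 1 − 0.95^k. With common correlation ρ, it is 1 minus the probability that all k equicorrelated standard normal statistics lie within ±1.96, found by numerical integration.

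| Tests k | ρ = 0 (upper bound) | ρ = 0.5 | ρ = 0.8 | ρ = 0.9 |
|---|---|---|---|---|
| 2 | 9.8% | 9.1% | 7.8% | 7.0% |
| 4 | 18.5% | 15.6% | 11.4% | 9.4% |
| 12 | 46.0% | 31.9% | 18.6% | 13.5% |

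Every cell exceeds 5%.

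**4. Power if all must succeed.** Simulated t-tests, 54 per arm, effect 10/16 = 0.625 SD on every measure, each test at 0.05:

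| Requirement | ρ = 0.5 | ρ = 0.8 | ρ = 0.9 |
|---|---|---|---|
| Total arc at both visits | 82.5% | 85.1% | 86.3% |
| All 4 ROM tests | 73.1% | 79.6% | 82.7% |

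No power can be computed for a rule that includes the instruments, because the plan gives no effect or SD for them.

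**5. Power if both visits remain co-equal primaries for total arc.** Bonferroni at 0.05/2 = 0.025 gives 83.3% per visit with 54 per arm and 81.8% with 52. Restoring 90% per visit under Bonferroni would need 64 evaluable per arm (normal approximation). Hochberg, simulated with a 10 degree effect at both visits and ρ from 0.5 to 0.9, gives about 88% per visit with 54 per arm and about 87% with 52.

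**The case against.** The strongest reply is that the intent can be inferred. Outcome Measures names ROM alone as primary, and Power Analysis powers total ROM alone, so two of three sections agree that ROM leads and the instruments may simply be loosely labelled. That is a fair reading of intent. It still leaves the visit and the mode unnamed, and Statistical Analysis does not carry total arc through as the sole primary test. Even one ROM measure tested at both visits gives 7.0% to 9.8%.

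A second reply is that the inflation depends on an any-one-wins rule which the plan never states, and that 46% needs both independence and all twelve tests. This stands as a caution: the ROM figures at correlations of 0.5 to 0.9 are more realistic than 46%. But no other success rule is stated, and the all-must-win alternative misses the 90%.

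Third, the count of four takes one measurement mode. Testing both active and passive motion would make eight ROM tests, with 33.7% under independence and 25% at correlation 0.5. The Table 3 shell also has rows for flexion below 90 and below 80 degrees. So 18.5% is an upper bound only for the four tests that Statistical Analysis lists.

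Finally, eligibility and Table 3 are framed around flexion, so a sponsor might prefer terminal flexion as primary. That choice is open, but the stated sample size was calculated for total ROM. Terminal flexion would need its own difference and SD.

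**Conclusion.** The concern holds. The contradiction is in the current text of two sections and depends on no assumption. The stated 54 per arm is right for one test of total ROM, but the plan does not make that test the deciding one. Under an any-one-wins rule the 5% becomes 9.4% to 18.5% for the four ROM tests, or 13.5% to 46% for all twelve. Under an all-must-win rule the 90% becomes 83% to 86% for total arc at both visits, or 73% to 83% for all four ROM tests. The sizes rest on assumed correlations (0 to 0.9 for false positives, 0.5 to 0.9 for power), one score per instrument, and an effect of 0.625 SD on each ROM measure. The direction does not change anywhere in those ranges. This must be fixed, because it determines what counts as a positive trial.

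**What to change.** Use one definition in both Outcome Measures and Statistical Analysis:

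- **Single primary endpoint:** total arc of motion, in one named mode (active or passive), at one named visit, two-sided 0.05, with one named analysis method. Power is 89.6% with 54 evaluable per arm and 88.4% with 52.
- **Second in fixed sequence:** total arc at the other visit, tested at 0.05 only if the first is significant. With 54 per arm the chance that both succeed is the 83% to 86% shown above.
- **Secondary in both sections:** terminal flexion, extension, KSS, SF-12v2, KOOS and PROMIS-29, reported with confidence intervals. Give the flexion-threshold rows in Table 3 a stated role as well.
- **If both visits stay co-equal primaries:** state the rule (Bonferroni or Hochberg) and quote its own power from step 5.

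The cost is wording only, with no new data and no change to the stated sample size, provided endpoint, mode and visit are fixed before outcome data are examined. Statistical Analysis mixes past and future tense, so the stage of the trial is unclear. If outcome data have already been seen, the choice must be dated and labelled as made afterwards. The price to the sponsor is that success can no longer rest on whichever measure or visit happens to reach p < 0.05.
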